**Table 2. Secondary Endpoint Overall Survival Censoring Rules:**

|       |  | Date of event/ censoring            | Censoring |
|-------|--|-------------------------------------|-----------|
| Alive | Post baseline assessments performed    | Date subject last known to be alive | Yes       |
|       | No post baseline assessments performed | Date of randomization               | Yes       |
| Dead  |  | Date of death                       | No        |

**Table 3. Sensitivity Analysis Disease-Free Survival by Investigator Assessment Censoring Rules:**

|   |   | Date of event/ censoring  | Censoring |
|---|---|---|-----------|
| No Investigator confirmed recurrence or occurrence of secondary malignancy or death | Post baseline assessments performed               | Date of last local imaging assessment prior to receiving anti-tumor therapy if applicable | Yes       |
|   | No post baseline assessments performed            | Date of randomization   | Yes       |
| Investigator confirmed  | Baseline scan evaluated by the investigator shows | Date of randomization   | No        |

Document: C:\Users\q764206\AppData\Local\Microsoft\Windows\Temporary Internet Files\Content.Outlook\GWW33WM3\ATLAS\_SAPFinal v8.0\_06MAR2018.docx  
 Author: [name] (Updated [name]; [name]; [name], [name]) Version Number: Final 8.0

Version Date: 06MAR2018

Template No: CS\_TP\_BS016 – Revision 2 Reference: CS\_WI\_BS005  
 Effective Date: 01Feb2010

Statistical Analysis Plan

|   |   |  |     |
|---|---|--|-----|
| recurrence or secondary malignancy or death | presence of disease   |  |     |
|   | Further anti-tumor therapy received after randomization and before recurrence or occurrence of secondary malignancy or death (Subject does not have two or more consecutively missed local imaging assessments immediately prior to recurrence, secondary malignancy or death)* | Date of last local imaging assessment prior to receiving anti-tumor therapy  | Yes |
|   | Further anti-tumor therapy received after randomization and before recurrence or occurrence of secondary malignancy or death and subject had two or more consecutively missed local imaging assessments immediately prior to recurrence, secondary malignancy or death)*        | Date of last local imaging assessment prior to the two consecutively missed scans and prior to receiving anti-tumor therapy* | Yes |
|   | No anti-tumor therapy received after randomization (Subject did not have two or more consecutively missed local imaging assessments)*   | Date of investigator confirmed recurrence or occurrence of secondary malignancy or death, whichever occurred first           | No  |
|   | No anti-tumor therapy received after randomization but subject had two or more consecutively missed local imaging assessments*  | Date of last local imaging assessment before two consecutively missed local imaging assessments*                             | Yes |

\*Additional details regarding the definition of two or more consecutively missed scans can be found in Appendix B. For subjects who died prior to missing two scheduled assessments, they will be coded as an event at the date of death and will not be censored as long as no anti-tumor therapy was given after randomization and before death.

**Table 4. Sensitivity Analysis Disease-Free Survival by Independent Review Committee without Censoring Subjects for Anti-tumor Therapy or for two or more consecutively missed or not readable scans**

**Censoring Rules:**

|           |   |                 |           |
|-----------|---|-----------------|-----------|
| Document: | C:\Users\q764206\AppData\Local\Microsoft\Windows\Temporary Internet Files\Content.Outlook\GWW33WM3\ATLAS_SAPFinal v8.0_06MAR2018.docx |                 |           |
| Author:   | [name] (Updated [name]; [name]; [name], [name])  | Version Number: | Final 8.0 |
|           |   | Version Date:   | 06MAR2018 |

Template No: CS\_TP\_BS016 – Revision 2  
 Effective Date: 01Feb2010

Reference: CS\_WI\_BS005

Statistical Analysis Plan

|  |   | Date of event/ censoring   | Censoring |
|--|---|--|-----------|
| No IRC confirmed recurrence or occurrence of secondary malignancy or death | Post baseline assessments performed     | Date of last IRC reviewed scan   | Yes       |
|  | No post baseline assessments performed  | Date of randomization  | Yes       |
| IRC confirmed recurrence or occurrence of secondary malignancy or death    | Baseline scan shows presence of disease | Date of randomization  | No        |
|  |   | Date of IRC confirmed recurrence or occurrence of secondary malignancy or death, whichever occurred first* | No        |

\* Note: For subjects for whom there is site confirmation of recurrence or occurrence of secondary malignancy in the absence of IRC imaging confirmation, the date of IRC confirmation from histo-/cytopathology specimens will be selected as the date of event if available. For subjects for whom the IRC sees a finding on a scan that requires confirmation but an additional scan is not provided, if there is a subsequent pathology report available the pathology report could be the confirmation of the disease seen on the scan. In this case the scan date should be used as the date of recurrence or secondary malignancy.

**Table 5. Sensitivity Analysis Disease-Free Survival by Independent Review Committee with Considerations for Start of New Anti-Tumor Therapy as Events**  
**Censoring Rules:**

|  |   | Date of event*/ censoring            | Censoring |
|--|---|--------------------------------------|-----------|
| No IRC confirmed recurrence or occurrence of secondary malignancy or death | Post baseline assessments performed, subject did not start a new anti-tumor therapy | Date of last IRC reviewed scan.      | Yes       |
|  | Post baseline assessments performed, subject did start a new anti-tumor therapy     | Date of start of anti-tumor therapy. | No        |
|  | No post baseline assessments performed  | Date of randomization                | Yes       |
| IRC confirmed recurrence or secondary                                      | Baseline scan shows presence of disease   | Date of randomization                | No        |
|  | Subject did not start a new   | Date of IRC confirmed                | No        |

Document: C:\Users\q764206\AppData\Local\Microsoft\Windows\Temporary Internet Files\Content.Outlook\GWW33WM3\ATLAS\_SAPFinal v8.0\_06MAR2018.docx

Author: [name] (Updated [name]; [name]; [name], [name])      Version Number:      Final 8.0

Version Date: 06MAR2018

Template No: CS\_TP\_BS016 – Revision 2  
 Effective Date: 01Feb2010

Reference: CS\_WI\_BS005

Statistical Analysis Plan

|                     |   |   |     |
|---------------------|---|---|-----|
| malignancy or death | anti-tumor therapy (Subject did not have two or more consecutively missed/not readable IRC reviewed scans immediately prior to recurrence, secondary malignancy or death)**   | recurrence or occurrence of secondary malignancy or death, whichever occurred first               |     |
|                     | Subject did not start a new anti-tumor therapy (Subject had two or more consecutively missed/not readable IRC reviewed scans immediately prior to recurrence, secondary malignancy or death)**  | Date of last IRC reviewed scan before two consecutively missed/not readable IRC reviewed scans**  | Yes |
|                     | Subject did start a new anti-tumor therapy before IRC confirmed recurrence or secondary malignancy or death (Subject did not have two or more consecutively missed/not readable IRC reviewed scans immediately prior to recurrence, secondary malignancy or death or immediately prior to new anti-tumor therapy)** | Date of start of new anti-tumor therapy   | No  |
|                     | Subject did start a new anti-tumor therapy before IRC confirmed recurrence or secondary malignancy or death (Subject had two or more consecutively missed/not readable IRC reviewed scans immediately prior to new anti-tumor therapy)**  | Date of last IRC reviewed scan before two consecutively missed/not readable IRC reviewed scans ** | Yes |

\* Note: For subjects for whom there is site confirmation of recurrence or occurrence of secondary malignancy in the absence of IRC imaging confirmation, the date of IRC confirmation from histo-/cytopathology specimens will be selected as the date of event if available. For subjects for whom the IRC sees a finding on a scan that requires confirmation but an additional scan is not provided, if there is a subsequent pathology report available the pathology report could be the confirmation of the disease seen on the scan. In this case the scan date should be used as the date of recurrence or secondary malignancy.

\*\*Additional details regarding the definition of two or more consecutively missed or inadequate scans can be found in Appendix B. For subjects who died prior to missing two scheduled assessments, they will be coded as an event at the date of death and will not be censored.

Document: C:\Users\q764206\AppData\Local\Microsoft\Windows\Temporary Internet Files\Content.Outlook\GWW33WM3\ATLAS\_SAPFinal v8.0\_06MAR2018.docx  
 Author: [name] (Updated [name]; [name]; [name], [name]) Version Number: Final 8.0

Version Date: 06MAR2018

Template No: CS\_TP\_BS016 – Revision 2  
 Effective Date: 01Feb2010

Reference: CS\_WI\_BS005

Statistical Analysis Plan

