# 9.2. Efficacy Analysis

## 9.2.1. Analysis of Primary Endpoint

DFS based on the IRC review of tumor assessments (by imaging or histo-/cytopathology reports in the absence of IRC imaging confirmation) is the primary endpoint in this study. Factors (and levels in each factor) used in the stratified log-rank test will be stated in the SAP.

The median DFS along with corresponding 95% CI will be estimated for each arm using Kaplan-Meier (KM) methods. The hazard ratio (Arm A/Arm B) will be estimated by proportional Hazard regression stratified by the factors used in the stratified log-rank test, and with treatment in the model. The DFS rates at 2 years and 5 years will also be estimated for each arm.

The following sensitivity analyses will be performed for DFS:

- DFS defined as in the primary analysis but based on local investigator assessment rather than IRC assessment. The earlier of the tumor scan date and the date of collection of histo-/cytopathology specimen (where applicable) confirming recurrence or secondary malignancy will be used.
- DFS based on IRC review defined as in the primary analysis but without censoring patients who receive further anti-tumor therapy or missed 2 or more consecutive tumor scans prior to recurrence or occurrence of a secondary malignancy or death. In other words, patients receiving further anti-tumor therapy or missing 2 or more consecutive tumor scans before disease recurrence or occurrence of a secondary malignancy or death will be assigned with DFS events at the first date of recurrence or occurrence of a secondary malignancy or death. In the absence of DFS event, DFS time will be censored at the date of last scan prior to the time of analyses. Patients alive who do not have post baseline disease assessment will have their DFS times censored at randomization.
- DFS based on IRC review defined as in the primary analysis but considering start of new anti-tumor therapy prior to recurrence, occurrence of secondary malignancy or death as events at the time of new anti-tumor therapy.

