**Statistical Analysis Plan**

---

a3: number of times agreement on event but INV declares event earlier than IRC Review;  
 $N = a+b+c+d$ .

The following measure of discordance will be calculated per arm:

- Total Event Discrepancy Rate:  $(b+c) / N$
- Early Discrepancy Rate (EDR):  $(a3+b) / (a+b)$
- Late Discrepancy Rate (LDR):  $(a2+c) / (a2+a3+b+c)$
- Overall Discrepancy Rate:  $(a2+a3+b+c) / N$

A window of 28 days will be used in determining agreement on timing of an event. Specifically, if the data or recurrence by the IRC is within +/- 28 days of the data of recurrence by the investigator these cases will be considered as ‘agreement on the timing and occurrence or an event’.

- DFS based on IRC Without Censoring for New Cancer Therapy or Missed Assessments: DFS based on IRC review, as defined for the primary analysis, but without censoring subjects who:
  - receive further anti-tumor therapy, or
  - have two or more consecutively missed or not readable scans immediately prior to recurrence, or occurrence of a secondary malignancy, or death.

In other words, a subject who meets the above criteria will be assigned a DFS event at the first date of recurrence or occurrence of a second primary cancer or death. In the absence of a DFS event, DFS time will be censored at the date of last scan prior to the time of analysis. Subjects alive who do not have post-baseline disease assessment will have their DFS times censored at randomization. (Refer to Table 4 of Appendix A for censoring rules.)

- Start of New Anti-tumor Therapy as DFS Event: DFS based on IRC review, as defined for the primary analysis, but utilizing the start date of new anti-tumor therapy as a DFS event. (Refer to Table 5 of Appendix A for censoring rules.)
- DFS at Scheduled Assessments: DFS based on IRC review, as defined for the primary analysis, but instead assigning the dates for events and censoring at the scheduled scan dates instead of the actual scan dates. Specifically, events that occur within +/- 4 weeks of a scheduled scan will be considered an event at the scheduled scan. Events outside the 4-week window will be counted as events at the next scheduled scan time and censoring outside the 4-week window would be censored at the previous scheduled scan. If, however, the event is death or disease at baseline, the date of death or date of randomization respectively will be used as the event date unless anti-tumor therapy was

---

|           |   |                 |           |

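### SAP Table 5, which should count new anti-tumor therapy as a DFS event at its start date, leaves some therapy starters without a rule and gives others conflicting ones

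*SAP*

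**What the plan says.** Protocol 9.2.1 lists a sensitivity analysis of IRC-based DFS "considering start of new anti-tumor therapy prior to recurrence, occurrence of secondary malignancy or death as events at the time of new anti-tumor therapy". SAP 7.3.1 repeats it, "utilizing the start date of new anti-tumor therapy as a DFS event", and sends the reader to Appendix A, Table 5 for the rules.

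Table 5 has two blocks.

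- **No IRC event and no death.** A patient in the row "Post baseline assessments performed, subject did start a new anti-tumor therapy" is an event at the therapy start date. A patient in the row "No post baseline assessments performed" is censored at randomization, and that row does not mention therapy.
- **IRC event or death.** Two rows concern patients who started therapy first. One makes therapy start the event, provided there was no run of two or more missed or unreadable scans "immediately prior to recurrence, secondary malignancy or death or immediately prior to new anti-tumor therapy". The other censors, and its condition is "Subject had two or more consecutively missed/not readable IRC reviewed scans immediately prior to new anti-tumor therapy".

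The double-asterisk note under Table 5 says of patients who die before missing two scheduled assessments that "they will be coded as an event at the date of death and will not be censored". The parallel notes under Tables 1 and 3 restrict this to patients who received no anti-tumor therapy between randomization and death. The Table 5 note has no such restriction.

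**The concern.** The primary analysis censors patients at the last scan before new therapy. If therapy is started because the investigator sees disease that the IRC has not confirmed, that censoring may be informative. This sensitivity analysis is one of the checks on that. Its event happens on the day therapy starts, so only what came before that day, including scans missed before it, should decide how the patient is coded.

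Table 5 makes the coding depend on what happens afterwards: whether scans were missed after therapy, and whether the patient later recurred or died. Two programmers working from the same data could reach different event counts and different event dates.

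**Working it through.** There is no figure in the plan to reproduce; this is a question of whether the rows cover every case. Set aside patients with disease at baseline by IRC, who are events at randomization. For patients who start new therapy, write L for the last evaluable scan, T for therapy start and E for a later IRC event or death. Let A mean a run of two or more missed or unreadable scans just before E, and B such a run just before T.

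Appendix B gives the limits. In Scenario 1 (last scan at least 16 weeks before the 3-year date) a run exists beyond 16 + 16 + 2 = 34 weeks after L. In Scenario 2 it is 16 + 26 + 2 = 44 weeks.

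The event row can be read strictly (neither A nor B) or loosely (not both). Going through the combinations:

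| Later IRC event or death | Any post-baseline scan | A | B | Strict reading | Loose reading |
|---|---|---|---|---|---|
| yes | either | no | no | event at T | event at T |
| yes | either | yes | no | **no row** | event at T |
| yes | either | no | yes | censored | **event row and censoring row** |
| yes | either | yes | yes | censored | censored |
| no | yes | n/a | no | event at T | event at T |
| no | yes | n/a | yes | event at T | event at T |
| no | no | n/a | no or yes | censored at randomization | censored at randomization |

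1. **Missing row.** On the strict reading, which is the natural one, A without B has no row. In Scenario 1, with no readable scan between T and E, this is any patient with T − L ≤ 34 weeks and E − L > 34 weeks. Without the later event, the same patient is an event at T (line 5). The loose reading closes this gap but places patients with B and not A in two contradictory rows (line 3). The wording fails either way.
2. **Two dates for one death.** Take line 1 with E a death before two missed scans. The row dates the event at T; the note dates it at E. If scanning stopped at T, then in Scenario 1 E − L ≤ 34 weeks, so E − T ≤ 34 weeks (44 in Scenario 2). If scanning continued after T, these limits do not bound the difference.
3. **Never scanned after baseline.** The last line censors at randomization although therapy started, against Protocol 9.2.1 and SAP 7.3.1.
4. **Opposite handling of B.** Scans missed before therapy lead to censoring on the strict reading if an IRC event or death follows (lines 3 and 4), but to an event at T if none follows and some post-baseline scan was done (line 6).

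The gap in item 1 can be reached without a protocol deviation. Protocol 5.3.4.2 and 5.3.4.3 say that patients taken off treatment for intolerable toxicity have regular tumor assessments until recurrence, a secondary malignancy or the start of new treatment. Scanning may therefore end at T, and a death more than 34 weeks after L then falls in the gap. Unreadable scans count towards a run as well.

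**The case against.** The strongest reply is that the general text settles the matter. Protocol 9.2.1 and SAP 7.3.1 both make therapy start the event, and DFS runs to the first event, so a sensible programmer would code T in the gap and ignore the later death date. This shows the intent. It does not settle the coding, because SAP 7.3.1 defers to Table 5, SAP Section 1 says the SAP supersedes the protocol, and the general text is silent on missed scans.

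Several limits on the point do stand.

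- A reader might infer that the analysis loses the events it exists to count. No row censors the patients in the gap; they are unassigned. Most combinations without missed scans are coded as intended, and no direction of bias is shown.
- A reader might infer that everyone who starts therapy before a first scan is censored at randomization. That is close to the primary rule in SAP 5.1. In Table 5 it reaches only patients with no post-baseline assessment at all and no IRC event or death; the row follows a convention used across the Appendix A DFS tables.
- A reader might take the typical case to be a recurrence called by the investigator, after which scans lapse. Protocol 5.5.2 and 7.1 require scans to continue in that situation until the IRC determines recurrence or a secondary malignancy, so lapsed scans there are a deviation. The toxicity route above does not have that problem.
- A reader might put a number on it. If 3–6% of 700 started therapy without IRC confirmation and 30–50% of these later died or recurred after missed scans, the gap would hold 700 × 0.03 × 0.30 ≈ 6 to 700 × 0.06 × 0.50 = 21 patients. Neither range has a source in the documents. Dividing by 245 would also mislead, since the primary rules in Table 1 censor these patients.
- Other analyses look at the same question. Table 4 drops censoring for therapy and for missed scans, so it counts the later event. Table 3 counts an investigator-called recurrence, absent missed local scans beforehand.

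**Conclusion.** Table 5 does not implement the analysis that Protocol 9.2.1 and SAP 7.3.1 define. On its natural reading one group of therapy starters has no row, on the looser reading another group has two, and on either reading the three further conflicts remain. This is more than missing detail, because the note and the randomization row, as written, contradict the definition.

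The size is unknown: the documents give no rate of new therapy before an IRC event and no rate of missed scans after it. The effect is confined to one of several sensitivity analyses. The primary test, the 245-event trigger, the interim and final boundaries and alpha are unaffected. The conclusion rests on the table wording and on the Appendix B limits, not on any assumed rate. The change should be made because the check is promised in the protocol and the repair costs almost nothing.

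**What to change.** Amend Table 5 in four places:

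- **(a)** In the event row for patients who started therapy before an IRC event or death, strike the limb about scans missed before the later recurrence, malignancy or death. Only scans missed before therapy then count. With B absent the patient is an event at T; with B present the patient is censored. The two rows become exclusive and complete.
- **(b)** Split the row for patients with no post-baseline assessment. If new therapy was started, the patient is an event at T, subject to the same rule on scans missed before therapy; otherwise censoring at randomization stays.
- **(c)** Limit the double-asterisk note to patients who started no new anti-tumor therapy before death, in line with Tables 1 and 3.
- **(d)** Apply the same rule on scans missed before therapy in both blocks, so that a patient with B is handled alike whether or not an IRC event or death follows.

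The cost is a few cells and one note in one SAP table, with matching program code. No new data are needed: the rules use therapy start dates and scan dates, and Protocol 5.5.1 already has anti-tumor therapy recorded beyond 28 days after last treatment. The change is best made before anyone analysing the data is unblinded.

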**Table 6. Disease-Free Survival by Independent Review Committee Censoring Only at Scheduled Visits**

**Censoring Rules:**

|   |  | Date of event*/ censoring  | Censoring |
|---|--|---|------------------|
| No IRC confirmed recurrence or occurrence of secondary malignancy | Post baseline assessments performed  | Date of last scheduled IRC reviewed scan prior to receiving anti-tumor if applicable  | Yes              |
|   | No post baseline assessments performed   | Date of randomization   | Yes              |
| IRC confirmed recurrence or secondary malignancy or death         | Baseline scan shows presence of disease  | Date of randomization   | No               |
|   | Further anti-tumor therapy received after randomization and before recurrence or occurrence of secondary malignancy or death (Subject did not have two or more consecutively missed/not readable IRC reviewed scans) | Date of last scheduled IRC reviewed scan prior to receiving anti-tumor therapy  | Yes              |
|   | Further anti-tumor therapy received after randomization and before recurrence or occurrence of secondary malignancy or death (Subject did have two or more consecutively missed/not readable IRC reviewed scans)     | Date of last scheduled IRC reviewed scan prior to receiving anti-tumor therapy and before two consecutively missed/not readable IRC reviewed scans        | Yes              |
|   | No anti-tumor therapy received after randomization (Subject did not have two or more consecutively missed/not readable IRC reviewed scans)   | Date of scheduled IRC assessment which confirmed recurrence or occurrence of secondary malignancy. If event is death then the date of death will be used. | No               |
|   | No anti-tumor therapy received after randomization (Subject did have two or more consecutively missed/not readable IRC reviewed scans)   | Date of last scheduled scan before two consecutively missed/not readable IRC reviewed scans   | Yes              |

\*Events that occur within +/-4 weeks of a scheduled scan will be considered an event at the scheduled scan. Events outside the 4-week window will be counted as events at the next scheduled scan time and

Document: C:\Users\q764206\AppData\Local\Microsoft\Windows\Temporary Internet Files\Content.Outlook\GWW33WM3\ATLAS\_SAPFinal v8.0\_06MAR2018.docx  
 Author: [name] (Updated [name]; [name]; [name], [name]) Version Number: Final 8.0

Version Date: 06MAR2018

Template No: CS\_TP\_BS016 – Revision 2 Reference: CS\_WI\_BS005  
 Effective Date: 01Feb2010

Statistical Analysis Plan

censoring outside the 4-week window would be censored at the previous scan.

